# 1 Trial Registration

## 1.1 Data set

Data Category	Information
Primary registry and trial identifying number	ClinicalTrials.gov
Date of registration in primary registry	TBD
Secondary identifying numbers	TBD
Source(s) of monetary or material support	N/A
Primary sponsor	Royal Victoria Regional Health Centre Research Institute
Contact for public queries	[name] NP, MN [[contact]]
Contact for scientific queries	[name] [name] [[contact]] Royal Victoria Regional Health Centre Research Institute, Barrie, Canada
Public title	Monthly versus daily buprenorphine formulations for treatment of opioid use disorder (OUD)
Scientific title	A pragmatic, multi-centre, open-label, randomized, 12-month, parallel group, superiority study to compare the effectiveness of subcutaneous buprenorphine depot (Sublocade®) vs daily sublingual buprenorphine with naloxone (Suboxone®) for the treatment of opioid use disorder ( STOP IT )
Country of recruitment	Canada
Health condition/problem studied	Agonist treatment, opioid use disorder
Intervention	Experimental: Sublocade® Active Comparator: Suboxone®
Key Inclusion and exclusion criteria	
Ages eligible: 18 to 65 years  Sexes eligible: Male; Female; Other  OUD eligible: Moderate-to-severe OUD as defined by the Diagnostic and Statistical Manual of Mental Disorders – Fifth Edition (DSM-V)  Induction/Stabilization therapy: Started and stabilized on Suboxone® (8mg/2mg to 24mg/6mg) for ≥7 days as determined by the following criteria:
 
1) No allergic reaction to buprenorphine, and

	
2) Clinical Opiate Withdrawal Scale score <math>\leq 12</math> (scale:0-48), and
 
3) Opiate Craving Visual Analog Scale score <math>\leq 20</math> (scale:0-100)
 
Inclusion criteria:
 
1) Written informed consent prior to enrolment
 
2) Must have an active Ontario Health Insurance Plan number
 
3) Contact information (telephone) available
 
4) Must have drug insurance coverage for either medication for duration of study or demonstrate ability to pay for the drug out-of-pocket
 
Exclusion criteria:
 
1) Receiving any investigational drug for OUD in previous 4 weeks
 
2) Congenital long QT syndrome or QT prolongation at baseline

Study type	
Interventional
 
Allocation: randomized 1:1
 
Intervention model: parallel assignment
 
Masking: open-label
 
Primary purpose: comparative effectiveness

Date of first enrollment	November 1, 2022
Target sample size	90
Recruitment status	Not yet started
Primary outcome(s)	
1) Difference in proportion of relapse-free weeks (time-frame; 12 months)
 
2) Difference in incidence rates of opioid-related healthcare utilization (time-frame; 12 months)

Key secondary outcome(s)	
1) Difference in Medication Satisfaction Questionnaire scores
 
2) Difference in World Health Organization Quality of Life – BREF Questionnaire scores
 
3) Difference in proportion of patients who attend <math>\geq 80\%</math> of scheduled clinic visits
 
4) Difference in opioid-related mortality proportions

## 1.2 Glossary of abbreviations and terms

CADTH	Canadian Agency for Drugs and Technologies in Health
COWS	Clinical Opiate Withdrawal Scale
DSM-V	Diagnostic and Statistical Manual of Mental Disorders – Fifth Edition
ICD-10-CA	International Statistical Classification of Diseases and Related Health Problems, Tenth Revision, Canada
ODU	Opioid use disorder
RAAM	Rapid Access Addiction Medicine
RVH	Royal Victoria Regional Health Centre
OAT	Opioid agonist therapy
ODB	Ontario Drug Benefit
SC-BPN-XR	Monthly subcutaneous buprenorphine
SL-BPN/NX	Daily sublingual buprenorphine/naloxone
SOPs	Standard operating procedures
VAS	Visual analog scale
WHOQOL-BREF	World Health Organization Quality of Life – Brief

## 2 Protocol Version

2021-November-30	Original (version 1.0)
2022-February-02	Revised (version 2.0)
2022-April-11	Revised (version 3.0)
2022-May-02	Revised (version 3.1)
2022-June-06	Revised (version 3.12)
2022-Aug-10	Revised (version 4.0)

## 3 Funding

All clinical services provided at the study sites (RAAM clinics), including staff salaries, equipment and consumables will be provided by the Royal Victoria Regional Health Centre. While there is no funding currently available for this study, some funding may be provided by the Royal Victoria Regional Health Centre Foundation at some later date to support data abstraction from the Institute for Clinical Evaluative Sciences.

##### 4.32 Roles and responsibilities

###### 4.32a Trial sponsor

The trial sponsor has no role in the design, analyses, interpretation of the data, writing or decision to report the study results. The sponsor will support study coordination and execution, including informed consent, enrollment, randomization, follow-up, administering questionnaires, data collection and storage, and monitoring. The study sponsor is responsible for taking all reasonable steps to ensure proper conduct of the clinical trial protocol, and that the clinical trial is performed in accordance with the International Council for Harmonisation for Good Clinical Practice (<https://www.ich.org/page/efficacy-guidelines#6>) and all applicable regulatory requirements.

#### *4.32b Trial funders*

The funding source (Royal Victoria Regional Health Centre/Royal Victoria Hospital Foundation) has no role in the design, execution, analyses, interpretation of the data, writing or decision to report the study results.

##### *4.41a Roles and responsibilities*

Design, conduct and analysis of **STOP-IT** study  
Preparation of protocol and revisions  
Preparation of electronic case report forms  
Publication of study reports  
Members of the trial and data management committees

##### *4.42b Roles and responsibilities*

Study planning  
Serious unexpected suspected adverse events reporting

Responsible for master file  
Site visits and monitoring  
Data quality and audit

## 5 Background and Rationale

### 5.1 Background

#### 5.1.1 Definition

Opioid use disorder (OUD) is defined in the Diagnostic and Statistical Manual of Mental Disorders, Fifth Edition (DSM-V) as a “problematic pattern of opioid use leading to clinically significant impairment or distress.” At least 2 of 11 pre-specified criteria must be present within a 12-month period to fulfil the DSM-V clinical definition. The DSM-V also uses the number of criteria present to categorize the severity of OUD, with mild OUD defined as having 2-3 criteria present, moderate OUD defined as having 4-5 criteria present, and severe OUD defined as having  $\geq 6$  criteria present.

#### 5.1.2 Epidemiology

Opioid use disorder and opioid-related deaths are increasing in Ontario and Canada. Compared to 2016, the age-adjusted opioid-related mortality rates in 2020 have increased by 161% in Ontario to 16.5 per 100 000 population and 114% in Canada to 16.7 per 100 000 population. Over 90% of these deaths were non-intentional, with 87% of all deaths involving fentanyl or fentanyl analogues. The majority of deaths occurred in males (75%) between the ages of 20 to 59 (88%). In the North Simcoe Muskoka Local Health Integration Network, the study region, there were 128 opioid-related deaths in 2020, an increase of 191% from 2016.

Like deaths, opioid-related healthcare utilization as measured by hospitalization and emergency department visits have also been increasing over the same time period. Compared to 2016, the age-adjusted opioid-related hospitalization rates in 2020 have increased by 19.8% in Ontario to 16.3 per 100 000 population and 5.9% in Canada to 17.8 per 100 000 population. Emergency room visits have increased by 166% during the same time period in Ontario to 84.5 per 100 000 population. In the North Simcoe Muskoka Local Health Integration Network, there were 622 emergency room visits and 128 hospitalizations that were opioid-related in 2020. The majority of hospitalizations and emergency room visits occurred in males (60%) between the ages of 20 to 59 (73%). The median length of hospitalization from 2016 to 2020 has remained unchanged at 3 days (Range 1 to 207 days), with an average cost per hospitalization of \$9 626 (CDN) (Range \$26 to \$296 831) (Source: The Ontario Case Costing Initiative; N=889 cases; Reporting period 2017 to 2018; ICD-10-CA codes F11.0 to F11.9 & T40.2; Accessed November 8, 2021).

## 5.13 Treatment

Opiate substitution treatment with either full (methadone) or partial (buprenorphine) opioid agonist therapy (OAT) has been shown to reduce self-reported opioid use or opiate positive urine drug tests compared to detoxification or psychological treatments. Opiate substitution treatment is also associated with a reduced risk of death. Relative adherence to OAT is highest when delivered as part of a comprehensive treatment program. Rapid access addiction medicine (RAAM) clinics have been established in Ontario to facilitate access to opiate substitution treatment as part of a comprehensive substance use disorder program.

There are 2 main opioid agonists used to treat OUD, methadone and buprenorphine. Buprenorphine has been approved by Health Canada for use in OUD, and is available in immediate (Suboxone®) and extended-release (Sublocade®) formulations. Monthly subcutaneous buprenorphine (SC-BPN-XR) has been shown to be non-inferior to daily sublingual buprenorphine/naloxone (SL-BPN/NX) for medication adherence and treatment retention. Other extended-release buprenorphine formulations have also demonstrated similar results (Table 1). The rationale for extended-release buprenorphine is to minimize the risk of suboptimal medication adherence, diversion, intravenous misuse and unintended exposures associated with buprenorphine/naloxone films and tablets.

**Table 1: Summary of comparative effectiveness of extended-release versus immediate release buprenorphine**

Author (Country/year)	Buprenorphine		Time Period (weeks)	Primary Outcome	Effect size (extended vs immediate) (mean difference (95% CI))
	Extended (N)	Immediate (N)			
Rosenthal et al. (USA/2013)	Implants (4 x 80mg) (N=114)	SL-BPN/NX (12- 16 mg/d) (N=119)	24	Mean % negative uds  + self-report opiod use (weeks 1 to 24)	31% vs 33.1% (-2.1 (-10.7, 6.2))
Rosenthal et al. (USA/2016)	Implants (4 x 80mg) (N=84)	SL-BPN/NX (≤8 mg/d) (N=89)	26	Responder proportion 	96.4% vs 87.6% (8.8% (0.009, ∞))
Lofwall et al. (USA/2018)	SC-BPN (8-32 mg/week) (weeks 1-11) SC-BPN (64-160 mg/month) (weeks 12-24) (N=215)	SL-BPN/NX (4- 24 mg/d) (weeks 1-11) SL-BPN/NX (8- 32 mg/d) (weeks 12-24) (N=213)	24	Mean % negative uds + self-report opiod use  Responder proportion 	35.1% vs 28.4% (6.7% (-0.1, 13.6))  37.0% vs 31.0% (3.0% (-4.0, 9.9))

 uds=urine drug screen; missing uds imputed as positive; denominator was 72 uds (3 per week x 24 weeks)

 responder proportion defined as participant with ≥4 of 6 months with negative uds + negative self-report (uds + self-report scheduled every month plus 4 random uds; total 10 uds + self-reports); all patients had been on SL-BPN/NX ≥ 12 months prior to enrollment; missing uds imputed as positive or negative with a 20% penalty for positive in extended-release group

 responder proportion defined as participant with  $\geq 2$  weeks uds/self-report negative of weeks 9-11 + uds/self-report negative at week 12, plus  $\geq 5$  weeks uds/self-report negative of weeks 12-24 + uds/self-report negative from weeks 21-24; missing uds imputed as positive

In Ontario, OAT prescriptions and prescribers have been increasing. Compared to 2016, buprenorphine prescription rates have increased by 61% to 1.91 patients per 1 000 population. While methadone still represents the most commonly prescribed OAT in Ontario, with a prescription rate of 2.88 patients per 1 000 population, its use has declined by 9% since 2016. The number of OAT prescribers in Ontario in 2020 was 4887, an increase of 112% from 2016. In 2020, 87.8% of OAT prescribers prescribed only buprenorphine (71.4%) or both buprenorphine and methadone (16.4%), while the remainder (12.2%) prescribed only methadone. In the North Simcoe Muskoka Local Health Integration Network, buprenorphine and methadone prescription rates are higher than the provincial average at 2.08 and 4.13 patients per 1 000 population, respectively. The number of buprenorphine only (N=259), buprenorphine and methadone (N=140) and methadone only (N=143) prescribers has also increased in the study region, with the largest increase in the buprenorphine only group (+123% from 2016 to 2020).

#### 5.14 Costs

The Canadian pharmaceutical costs of Sublocade® and Suboxone® differ substantially (Table 2).

**Table 2: Canadian costs of buprenorphine-based OAT**

Drug	Health Canada Approval Date	Dose	Monthly Costs (\$CDN)
Sublocade®	November 21, 2018	100 mg/0.5 ml	550
		300 mg/0.5 ml	550
Suboxone®	August 25, 2015	2 mg/0.5 mg	72
		8 mg/2 mg	77

The costs of both drugs are covered through the Ontario Drug Benefit (ODB) program. However, Sublocade® is limited for use in patients with moderate- to severe- OUD who have been stabilized on 8 to 24 mg/day of transmucosal buprenorphine/naloxone for at least 7 days and who are also receiving counselling and psychosocial supports by experienced healthcare providers in the diagnosis and management of OUD. Eligibility criteria for the ODB program are limited to patients aged 25 years and under or 65 years and older; or are enrolled in the Ontario Works, Ontario Disability Support Program or Trillium Drug Program; or are receiving professional home and community services; or are living in a long-term home or a home for special care. As a result, the majority of patients meeting criteria for Sublocade® use must pay for the drug out-of-pocket resulting in significant restriction to access for this population that has a high burden of chronic homelessness and poverty.

A recent pharmacoeconomic report by the Canadian Agency for Drugs and Technologies in Health (CADTH) concluded that the current evidence base for supporting cost-effectiveness of Sublocade® over buprenorphine/naloxone is limited by the absence of studies directly comparing the effectiveness of the two treatments on clinically important outcomes such as healthcare utilization. Additionally, the comparative effectiveness studies reviewed in Section 5.13 were all conducted in the United States, making inferences about Canadian settings such as the RAAM clinics and their clientele uncertain. With limited evidence and significant uncertainty, the CADTH analysis suggested that a price reduction of at least 73% would be required for Sublocade® to be a cost-effective alternative to buprenorphine/naloxone.

## 5.2 Rationale

An extended-release OAT formulation that can be safely delivered in RAAM clinics across Canada might prevent costly healthcare and poor outcomes in hundreds, if not, thousands of patients. A real-world (pragmatic) randomised study is therefore needed to compare the treatment effectiveness of Sublocade® versus Suboxone® in Canadian patients attending RAAM clinics for OAT for moderate- to severe-OUD. This study is needed to demonstrate the superior benefits of Sublocade® on important clinical outcomes such as reduced opioid and healthcare utilization in order to demonstrate its cost-effectiveness and justify expanded access to Sublocade® for this at-risk population.

## 5.3 Choice of Comparator

According to the Canadian and Ontario guidelines for OAT, transmucosal buprenorphine/naloxone is the first-line treatment for moderate- to severe-OUD. Suboxone® will be the active comparator in this study. The medically active ingredients in Suboxone® are buprenorphine, a partial  $\mu$ -opioid receptor agonist, and naloxone, a  $\mu$ -opioid receptor antagonist. Suboxone® (buprenorphine/naloxone) formulations approved for use in Canada come in sublingual tablets (SL) and soluble films (SF) in doses ranging from 2 mg/0.5 mg (SL/SF), 4 mg/1 mg (SF), 8 mg/2 mg (SL/SF), 12 mg/3 mg (SL/SF) and 16 mg/4 mg (SL). Both formulations can be administered sublingually, but the SF can also be administered buccally. The usual treatment course requires induction, stabilization, and maintenance phases, with the ultimate goal being weaning to abstinence if possible. For those patients attending any one of the study RAAM clinics who have been started on treatment with Suboxone® for moderate- to severe-OUD after discussion with their healthcare provider, those who have been stabilized on 8 mg to 24 mg/day of buprenorphine for at least 7 days will be eligible to be enrolled in the study. For those who are enrolled in the study and are randomly allocated to continue receiving Suboxone® for the remainder of the study period, their ongoing Suboxone® maintenance dosing will be determined by themselves and their healthcare provider through the usual processes of clinical care. In general, treatment with Suboxone® is directly observed by the pharmacist in a community pharmacy experienced with OAT during the induction and stabilization phases. Once stabilized, the patient and provider can negotiate unsupervised Suboxone® administration through varying amounts of take-home doses during the

maintenance phase. Initially, the unsupervised intervals are short, typically one to several days, and depending on patient compliance with treatment that includes counselling and RAAM clinic visits every one to two weeks, abstinence from other non-prescription opioid and non-opioid substances as determined through self-report and urine drug screens, and evidence of absence of withdrawal symptoms, the take-home intervals may be extended. Breakthrough doses of Suboxone® may also be prescribed during the maintenance phase if the patient is experiencing withdrawal symptoms. It is not expected that any patient in the maintenance phase of OAT with either Suboxone® or Sublocade® during the 12-month study period will be ready for an attempted wean to abstinence.

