## 10.1 Inclusion criteria

Patients eligible for the trial must comply with all of the following at randomization:

1. Ages 18 to 65 years old
2. OAT indicated for moderate- to severe-[OUD](#)
3. Attend a RAAM clinic in the North Simcoe Muskoka Local Health Integrated Network for opiate substitution treatment
4. Successfully completed induction and stabilization OAT with [Suboxone](#)® tablet or film defined as receiving 8mg/2mg to 24mg/6mg of [Suboxone](#)® for  $\geq 7$  days with no evidence of allergic reaction to [Suboxone](#)®, [Clinical Opiate Withdrawal Scale](#) (COWS) score  $\leq 12$  (scale:0-48) for  $\geq 24$  hours, and [Opiate Craving Visual Analog Scale](#) (VAS) score  $\leq 20$  (scale:0-100) for  $\geq 24$  hours
5. Must have an active Ontario Health Insurance Plan number
6. Must have a telephone that can receive calls, text messages or emails
7. Must have drug insurance coverage for either medication for duration of study or demonstrate ability to pay for the drug out-of-pocket

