## 15 Recruitment

The 4 RAAM clinics serve the entire North Simcoe Muskoka Local Health Integrated Network region, are owned and operated by the Royal Victoria Regional Health Centre and are administered by the same manager and medical lead (see Section 9 for details).

Each RAAM clinic will screen 100% of patients who successfully complete induction and stabilization with Suboxone® as this is the point at which patients might be eligible for enrollment and randomization. Screening will continue until the target population is achieved. There will be no fixed number of patients that must be recruited from any site, only that each

site will have a 1:1 allocation ratio between the treatment groups. The expectation is that 1 to 2 patients will be enrolled per week.

The RAAM clinic healthcare providers will be responsible for expressed consent in eligible patients. For those patients who provide expressed consent, the RAAM clinic healthcare providers will contact the study team and provide them with the patient's name and contact number and inform the patient that they will be contacted by the study team to further discuss the study. A study team member will contact the patient and arrange a meeting, either in person, telephone or videoconference, to determine eligibility and review the study and secure informed consent.

For patients who cannot travel to a laboratory to complete their screening bloodwork or electrocardiogram, arrangements will be made to have the screen completed at their home address at no charge to the patient.

Patients who are enrolled in the study at the Midland, Orillia, and Wasaga Beach RAAM clinic sites will now be able to receive their Sublocade® doses on-site. Previous to this study, those patients would have had to travel to the Barrie RAAM clinic site to receive Sublocade®. A taxi ride for this travel would be required as there is no bus or train that connects these sites, with the cost for a round trip in excess of \$150 (CDN) (personal communication, [name]).

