## 16 Allocation

### 16.1 Sequence generation

Participants will be randomly assigned to either Suboxone® or Sublocade® with a 1:1 allocation schema as per a computer-generated randomisation schedule stratified by RAAM clinic site and severity of OUD (moderate versus severe by DSM-V criteria) using permuted blocks of size 6 in each strata. A single block size was chosen since the next block size of 18 might be too large to allocate patients in a 1:1 ratio in the smaller RAAM clinics. The block size will not be disclosed to ensure concealment. Sufficient numbers of blocks will be prepared *a priori* to ensure sufficient coverage for all strata in the event that they have different sample sizes as there will be no *a priori* fixed ratio for enrollment in the different strata.

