## 20.11 Primary

### 20.11a Opioid positivity

We will use a 3-level hierarchical design to model the relapse-free weeks data where the observation for each week (Level 1) will be coded as binary; relapse-free week if urine drug screen and self-report is negative for non-prescribed opioid use, and otherwise relapse week if either is positive for non-prescribed opioid use. As described in Section 12.11, imputation of missing data will occur for those weeks in which a urine drug screen/self-report was not scheduled according to the results of the subsequent week's urine drug screen/self-report. Level 1 observations are clustered within individual participants (Level 2), which are nested within RAAM clinic sites (Level 3). We will analyse the outcome data using multi-level, mixed-effects logistic regression analysis with random effects estimated for the variance in the intercepts of both participant and clinic levels. The model will also include a random slope on the indicator for OUD severity (moderate versus severe) in the Level 2 random effects equation using an unstructured covariance structure between intercept and slope. We will also include clinic visit (week) and an interaction term between clinic visit and treatment. A sensitivity analysis will be conducted to compare this baseline model with an extended model that includes any baseline demographic or clinical variables that appear to be unbalanced at Level 1. The models will be compared using the likelihood-ratio comparison test for superiority. Post-regression analyses using *margins* command will be used to estimate difference in proportions of RFWs between treatment groups.

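### Eligibility sets no maximum on prior Suboxone treatment and time on Suboxone is neither listed as baseline data nor adjusted for, so the primary opioid comparison may lose some precision that is cheap to recover

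*Combined protocol and SAP*

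**What the plan says.** **Eligibility.** Section 5.3 states that "those who have been stabilized on 8 mg to 24 mg/day of buprenorphine for at least 7 days will be eligible to be enrolled". Section 10.1, item 4, begins "Successfully completed induction and stabilization OAT with" Suboxone and adds limits on withdrawal and craving scores. It gives no upper limit on time on treatment, and neither do section 1.1 or the exclusion list in section 10.2.

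**Recruitment.** Section 15 ties screening to the end of stabilization on the comparator drug: "Each RAAM clinic will screen 100% of patients who successfully complete induction and stabilization with" it. The reason given there is that eligibility can first arise at that stage. The section 13 timeline places screening one week before randomization.

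**Randomization.** In section 16.1, allocation is "stratified by RAAM clinic site and severity of OUD (moderate versus severe by DSM-V criteria"). Section 8 names the same two factors.

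**Primary opioid model (section 20.11a).** Random intercepts for participant and clinic, a random slope on severity, and: "We will also include clinic visit (week) and an interaction term between clinic visit and treatment". Further covariates enter only through a sensitivity model that "includes any baseline demographic or clinical variables that appear to be unbalanced at Level 1".

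**Baseline data.** The section 18.11a tables are collected before induction. They list prescribed medications, but no Suboxone start date or duration. Sections 18.11b and 18.12 list none either.

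**The concern.** A patient who reached stability last week and one who has been stable for a year both meet the criteria as written. If time on treatment predicts relapse-free weeks, the difference between such patients adds to the between-patient variance of a comparison with 45 per arm. A chance excess of long-stable patients in one arm would also move the estimated difference. The section 20.11a sensitivity model has no listed duration variable to examine for imbalance.

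Long-stable patients are plausible. Section 9 reports 346 opioid-related consultations at these clinics since April 2021. Section 15 says three sites can now give Sublocade on site, where patients previously faced a round trip costing more than $150. Existing Suboxone patients there have a new reason to enrol.

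**Working it through.** **1. The plan's own figures.** Inputs from sections 14.2 and 14.4: 0.30 versus 0.45, two-sided 0.05, 45 per arm, 5 measures per patient, correlations 0.8 (within patient) and 0.025 (within clinic), 4 clinics.

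- Simple Z-test, unpooled, 80% power: (1.960 + 0.842)² × (0.30×0.70 + 0.45×0.55) / 0.15² = 160 per group. This reproduces section 14.2.
- Three-level variance factor: 1 + 4×0.8 − 5×0.025 = 4.075. With 45 per arm the standard error is √(0.4575 × 4.075 / (5×45)) = 0.091. Under the pooled null it is √(2 × 0.375 × 0.625 × 4.075 / 225) = 0.092.
- Power is Φ((0.15 − 1.960×0.0921)/0.0910) = 37%, not the stated 90.0%. By the same formula 90% needs 176.7 per arm. Since 176.7/4 = 44.2, the stated 45 matches a number per arm per clinic.

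That is a separate and larger problem. It matters here only as the baseline for judging the covariate.

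**2. Gain from adjusting for duration alone.** The documents give no mix and no duration effect, so both are assumed. Let a share f be long-stable, let recent starters average 0.30 (the planning value), and let the gap between the groups be D. Use 24 tests per patient and apply the 0.8 correlation within each group.

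- Variance due to duration: B = f(1−f)D²
- Remaining variance of a patient's mean: W = v(0.8 + 0.2/24), where v is p(1−p) averaged over the two groups
- Share explained: R² = B/(B+W). Equivalent gain in patients: R²/(1−R²) = B/W
- SD of the shift in the estimate from chance imbalance: D√(2f(1−f)/45)

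| D | f | B | W | R² | Gain | SD of shift |
|---|---|---|---|---|---|---|
| 0.20 | 0.1 | 0.0036 | 0.173 | 2.0% | 2.1% | 0.013 |
| 0.20 | 0.3 | 0.0084 | 0.179 | 4.5% | 4.7% | 0.019 |
| 0.40 | 0.1 | 0.0144 | 0.170 | 7.8% | 8.5% | 0.025 |
| 0.40 | 0.3 | 0.0336 | 0.170 | 16.5% | 19.8% | 0.039 |
| 0.55 | 0.1 | 0.0272 | 0.163 | 14.3% | 16.7% | 0.035 |
| 0.55 | 0.3 | 0.0635 | 0.150 | 29.8% | 42.4% | 0.053 |

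The gain and the shift are one cost seen twice: the unadjusted standard error already allows for the imbalance.

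**3. Gain once baseline urine and self-report are in the model.** Section 13 schedules both at weeks −1 and 0. Assume these two results share the 0.8 correlation with each other and with later results. For the baseline mean x and the outcome mean y:

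- Var(x) = B + 0.9v, Var(y) = B + 0.8083v, Cov = B + 0.8v
- Residual variance given x: Var(y) − Cov²/Var(x)
- Residual variance given x and duration: v(0.8083 − 0.8²/0.9) = 0.0972v

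At D = 0.55, f = 0.3: v = 0.1853. The residual is 0.2133 − 0.2117²/0.2303 = 0.01858 without duration and 0.01801 with it, a gain of 3.2%. At D = 0.40, f = 0.1: v = 0.21, and the residuals are 0.02058 and 0.02042, a gain of 0.8%. Over these cases the baseline results alone explain 89% to 91% of the variance. With one baseline result instead of two, duration is worth 1.5% to 6.1%.

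**4. Effect on power at 45 per arm.** Multiplying the variance in step 1 by (1 − R²) gives 38.5% at R² = 0.05, 40.2% at 0.10, 44.4% at 0.20 and 49.4% at 0.30.

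**The case against.** The strongest case against is that the documents describe a loose criterion, not a mixed population. Section 6 concerns patients seeking or referred for treatment and then moving to maintenance. Section 15 screens at the end of stabilization. Section 11.1 has all Suboxone dosing directly observed for the first two weeks, which section 5.3 describes as usual for the early phases. This stands: a substantial long-stable share is permitted, not shown.

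Four stronger readings are tempting, and the documents do not support them.

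- **Table 1 shows that duration is strongly prognostic.** The daily-buprenorphine arm reached 87.6% in the study of which footnote 2 says "all patients had been on SL-BPN/NX ≥ 12 months prior to enrollment", against 28.4% and 33.1% in the other two. But 87.6% is a responder proportion and the others are mean percentages negative, with different handling of missing tests. That study also used at most 8 mg/day, and its title in the reference list restricts it to abstinent adults. The contrast does not isolate duration.
- **The comparison is biased.** Randomization keeps it unbiased, and imbalance that arises by chance is part of the ordinary sampling error.
- **Baseline urine results cannot stand in for duration, because both kinds of patient can test negative at entry.** Step 3 shows otherwise under the plan's own 0.8 correlation. The section 20.11a model omits baseline urine too, however, so the precision is lost either way.
- **The sensitivity model could never use duration.** The eligibility screen is a case report form item in section 13 and must confirm the 7 days, so the date may well be at hand. What is missing is any statement that it is kept as a baseline variable.

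**Conclusion.** The point holds as a cheap improvement, not as the correction of an error. No maximum duration is set, and time on Suboxone appears in no stratum, model term or listed baseline variable.

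The precision at stake is unknown. With 10% to 30% long-stable patients it is worth about 2% to 5% more patients at a 0.20 gap and 9% to 42% at gaps of 0.40 to 0.55. At those larger gaps it falls to about 1% to 3% once two baseline results are adjusted for. The last range assumes that baseline results correlate with later ones at 0.8; a weaker correlation would leave more for duration to explain. All the gains assume a clean two-group split on a linear scale, so they indicate the size of the benefit and do not predict what log(days) would achieve in a logistic mixed model.

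A reader might infer that adjustment would rescue the power. It would not: even at R² = 0.30, power at 45 per arm is about 49%.

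**What to change.** 1. Record the start date of the current Suboxone episode in REDCap at the eligibility check, where it is needed anyway to confirm the 7 days. Keep it as a baseline variable. It would also show how old the pre-induction baseline data are at randomization.
2. Tabulate time on Suboxone at randomization by arm.
3. In section 20.11a, pre-specify log(days on Suboxone at randomization) as a fixed covariate in the primary model, whether or not it looks unbalanced. Preferably add the urine and self-report result already scheduled at weeks −1 and 0, which under the plan's correlation is the stronger covariate. Naming both in advance avoids data-driven selection in a trial whose analysts are unmasked (section 17).

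The cost is one data field and one or two model degrees of freedom. Eligibility and treatment do not change. The sample size in section 14.4 needs separate attention.
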